8.3 Efficacy Analyses

8.3.1 Analyses of the Primary Endpoint

The purpose of this study is to assess the efficacy, safety and biomarker effects in an AD population that results from patients initiating ALZ-801 versus Placebo. The estimand, estimator, and estimate of this primary efficacy endpoint are described and defined in Table 16.

[figure not shown]
Table 16 Estimand, Estimator, and Estimate of Primary Efficacy Endpoint

	Population	FAS
	Variable	Change in ADAS-Cog 13 scores from baseline to Week 78
	Intercurrent	Potential intercurrent events include treatment discontinuation
pu	Events	and use of symptomatic AD medications. The "treatment-
maı		policy" strategy will be followed for the primary analysis,
Estimand		whereby the value for the endpoint of interest will be used
田		regardless of occurrence of intercurrent events.
		Supportive analyses based on "while-on-treatment" strategy will
		be performed to evaluate the impact of intercurrent events on
		efficacy with censoring of data after intercurrent events.

	Population-	The between treatment difference in the mean change from		
	level	baseline to Week 78 in ADAS-Cog 13 scores		
	Summary			
	Analysis	Mixed-Effect Model Repeated Measure (MMRM) model with		
 		fixed class effect terms for treatment group, gender, age group,		
atc		disease severity based on baseline MMSE (≤ 26 vs. > 26), use		
Estimator		of concomitant AD medications, visit, and treatment by visit		
Est		interaction and baseline ADAS-Cog 13 values as covariates.		
	Primary to	Between-treatment group comparison (effect in ALZ-801 minus		
	support the	effect in placebo):		
	estimand	LSM for the between-group difference		
ပ		• 95% CI of treatment difference		
Estimate		• p-value		
	Tributary	Within-treatment group comparison (effect at Week 78 minus		
	-	the value at baseline):		
		LSM for the within-group difference		
		• 2-sided 95% CI of the LSM		
		• p-value		

ADAS-Cog 13 scores are assessed at Day 1 (Baseline), and Weeks 13, 26, 52 and 78. Observed ADAS-Cog 13 scores including those from unscheduled visits and early discontinuation, are assigned analysis visits based on the visit window using the assessment's study days. After applying a visit window, there is only one non-missing or missing value for each analysis visit. These data are called observed data and the change from baseline in ADAS-Cog 13 scores (observed data) for efficacy analyses are derived by subtracting corresponding baseline value at each visit. Other efficacy endpoints derivation follows the same algorithm.

Unless otherwise specified, all primary efficacy analyses will be performed using the FAS population. Analyses of the primary endpoint of ADAS-Cog 13 will be performed with a likelihood based MMRM on treatment observed cases (OCs). The observed data set will consist of actual observations recorded at each visit and missing data is not explicitly imputed. The model terms will include treatment, the stratification factors of use of concomitant AD medications (AChEI or none), age group (50-65 years inclusive or > 65 years through 80 years), gender, disease severity based on baseline MMSE (≤ 26 vs. > 26), baseline ADAS-Cog 13 values, visit (VISIT), and treatment-by-visit interaction. The visit variable will be used to define the within-subject covariance for the repeated measures over time. The least squares mean (LSM) for each treatment at each visit will be generated together with its 95% confidence interval, and the LSM difference between ALZ-801 and placebo will also be calculated; together with its standard error, and the 2-sided 95% confidence interval. The MMRM has an inherent mechanism to "implicitly impute" missing values when calculating the LSM of treatment effects which assume missing at random (MAR). For the primary endpoint at 78 weeks, treatment comparisons will be done at the 0.05 significance level.

All data collected during the study will be used in the statistical analysis. Under the treatment policy strategy, measurements after occurrence of intercurrent events (subject withdrawal or dropouts for various reasons or use of symptomatic AD medications) will not be considered missing data and will be included in the primary analyses. For subjects who discontinue treatment prior to trial completion, every attempt will be made to have them continue with clinic visits and study assessments. Particular attention will be given to collecting Week 78 ADAS-Cog 13 assessments, regardless of when subjects discontinued treatment.

Note that only the post-baseline visits on which the endpoints are scheduled to be measured will be included in the model.

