4.1 Primary Clinical Outcome

The target study sample size was 300 subjects randomized or 150 subjects per treatment group, based on ADAS-Cog 13, the primary clinical outcome. The study completed enrollment with 325 randomized subjects. The ADAS-Cog 13 is a well-validated and widely-used measure of global cognition in AD observational studies and Phase 3 drug trials. This scale evaluates multiple cognitive domains including memory, language, praxis, orientation, and executive function. To improve the sensivity of ADAS-Cog in MCI patients, two additional items were added to the original 11-item scale, including delayed word recall and digit cancellation (Mohs 1997).

Study Sample Size

Sample size determination was based on ADAS-cog results from an AD trial with tramiprosate, the active agent in ALZ-801. These efficacy data were observed in Mild AD patients (baseline MMSE =22-26) with APOE4/4 genotype who received tramiprosate 150mg BID over 78 weeks (Abushakra 2017). The tramiprosate 150mg BID dose provides plasma exposures similar to ALZ-801 at 265mg BID, the dose used in the current study.

In the 78-week tramiprosate Phase 3 study, the APOE4/4 Mild AD patients showed approximately 5.0-point difference from placebo (benefit) on ADAS-Cog. Since this Phase 3

For the primary efficacy outcome of ADAS-Cog 13, this study is powered to detect a 3.0-point difference between the active ALZ-801 treatment and the placebo in the CBL to Week 78. An increase in ADAS-Cog scores denotes cognitive worsening. It is expected that the mean baseline ADAS-Cog 13 in both groups will be 22.0 (standard deviation [SD] 6.7), which is expected to increase by 6 points in placebo (CBL: 6.0, SD 5.6), and 3 points in the active drug arm (CBL: 3.0, SD 8.1). A sample size of 125 completed subjects per arm will provide > 90% power to detect a difference of 3 points on ADAS-Cog. The drop-out rate is estimated to be approximately 17% at 78 weeks, thus a total of 300 subjects enrolled would provide approximately 250 completers (125 per arm).

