The example SAS programming codes using MCMC method for non-monotone missing pattern, follow by regression method for monotone missing pattern are:

```
PROC MI DATA=DATAIN OUT=DATAOUT MONO NIMPUTE=100 SEED=999[to be
changed];
CLASS TREATMENT ACHEI AGEGRP GENDER DISSTAGE;
VAR TREATMENT ACHEI AGEGRP GENDER DISSTAGE BASE ... ; [insert
scheduled visits for ADAS-Cog 13 up to Week 78, i.e, V5 V7 ....
MCMC CHAIN=MULTIPLE IMPUTE=MONOTONE;
PROC SORT DATA=DATAOUT MONO;
BY IMPUTATION TREATMENT;
RUN;
PROC MI DATA-DATAOUT MONO OUT-DATAOUT REG SEED-999[to be changed]
NIMPUTE=1;
BY IMPUTATION;
CLASS TREATMENT ACHEI AGEGRP GENDER DISSTAGE;
VAR TREATMENT ACHEI AGEGRP GENDER DISSTAGE BASE ... ; [insert
scheduled visits for ADAS-Coq 13 up to Week 78, i.e, V5 V7 ...]
MONOTONE REGRESSION;
RUN;
```

The changes from baseline at all visits will be calculated from the imputed 100 sets of data. The MMRM model will be examined for each set of data. The results from the 100 sets of data will be combined via Rubin's rule to produce estimated LSMs and 95% CIs that incorporate the uncertainty from missing data. PROC MIANALYZE will be used. The example SAS programming codes are:

```
PROC SORT DATA=DATAOUT_REG;

BY _IMPUTATION_ TREATMENT;

RUN;

PROC MIXED DATA=DATAOUT_REG;

BY _IMPUTATION_;

CLASS TREATMENT(REF='PLACEBO') ACHEI AGEGRP GENDER DISSTAGE;
```

```
MODEL CHG =TREATMENT ACHEI AGEGRP GENDER DISSTAGE BASE VISIT TREATMENT*VISIT/SOLUTION;
REPEATED VISIT/SUBJECT=USUBJID TYPE=UN;
LSMEANS TREATMENT*VISIT /ALPHA=0.05 PDIFF CL;
ODS OUTPUT LSMEANS=LS DIFFS=LSDIFF;
RUN;
PROC SORT DATA=LSDIFF;
by _IMPUTATION_;
RUN;
PROC MIANALYZE PARMS(CLASSVAR=FULL) = LSDIFF;
CLASS TREATMENT;
MODELEFFECTS TREATMENT*VISIT;
ODS OUTPUT PARAMETERESTIMATES=DIFF_MI;
RUN;
```

Multipe Imputations (Missing Not at Random, MNAR)

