8.3.3 Analyses of Key Secondary and Other Secondary Endpoints

The same MMRM method applied to the primary efficacy endpoint will be used to evaluate the between-treatment difference for the key secondary endpoints and the other secondary endpoints using the FAS. The same treatment policy strategy as that applied to the primary efficacy endpoint will be used for the secondary efficacy endpoints analysis. Differences between the two treatment groups, the p-values, and the 2-sided 95% CIs will be calculated within the framework of MMRM. The model will include all terms as in the primary endpoint model except that the baseline values will be corresponding to the baseline value for each parameter. Note that only the post-baseline visits on which the endpoints are scheduled to be measured will be included in the model.

The main analysis population is the FAS. Similar sensitivity analyses as for primary endpoint will be repeated for the key secondary and other secondary endpoints. As supportive analysis, the key and other secondary endpoints will also be analyzed using the PPP, and CP. Additional sensitivity analyses using MMRM with Last Observation Carried Forward (LOCF) may be performed.

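### The primary MMRM gives baseline ADAS-Cog 13 one slope for all four visits; adding a baseline-by-visit term would protect Week 78 precision at almost no cost

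*SAP*

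**What the plan says.** The primary model has treatment, the four stratification factors, and then "baseline ADAS-Cog 13 values, visit (VISIT), and treatment-by-visit interaction" (SAP 8.3.1). Table 16 agrees: its fixed effects end with "interaction and baseline ADAS-Cog 13 values as covariates". The example code in SAP 8.3.2, written for the multiple-imputation sensitivity analysis, reads "MODEL CHG =TREATMENT ACHEI AGEGRP GENDER DISSTAGE BASE VISIT TREATMENT*VISIT/SOLUTION", with covariance statement "REPEATED VISIT/SUBJECT=USUBJID TYPE=UN". Protocol 10.7.2 lists the same terms. Treatment is the only factor allowed a separate effect at each visit.

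Four post-baseline visits share the baseline slope: "ADAS-Cog 13 scores are assessed at Day 1 (Baseline), and Weeks 13, 26, 52 and 78". SAP 8.3.3 carries the specification to the key and other secondary endpoints: "The model will include all terms as in the primary endpoint model", with each endpoint's own baseline substituted. None of the supportive or sensitivity analyses in 8.3.2 lets the baseline slope vary by visit.

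**The concern.** The outcome is change from baseline, so measurement error in the baseline score pushes the slope of change on baseline downwards, most visibly when little true change has occurred. Later, if more impaired subjects decline faster, the slope can rise. There is therefore a reason to expect unequal slopes, though the documents do not report any.

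With a single slope, the fitted value is a weighted average of the visit-specific slopes, with weights set by the covariance matrix and not by the visit of interest. If that average is not the Week 78 slope, part of any chance difference in baseline severity between arms stays in the Week 78 contrast as noise. That contrast is the primary test and the gatekeeper for A-IADL-W and CDR-SB, which would be fitted with the same constraint.

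**Working it through.** **The plan's own figure first.** SAP 4.1 expects that "the mean baseline ADAS-Cog 13 in both groups will be 22.0 (standard deviation [SD] 6.7"), that scores will "increase by 6 points in placebo (CBL: 6.0, SD 5.6"), and a change of 3.0 with SD 8.1 on drug. The pooled SD is sqrt((8.1² + 5.6²)/2) = sqrt(48.485) = 6.963. With 125 completers per arm, SE = 6.963 × sqrt(2/125) = 0.881. Two-sided 5% power is 92.6% for 3.0 points (SAP: above 90%) and 81.0% for 2.5 points (SAP: about 80%). Both reproduce.

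**Formulas.** Let b be the vector of true slopes at the four visits and S the residual covariance.
- Pooled slope under an unstructured MMRM: b_c = (1'S⁻¹b)/(1'S⁻¹1).
- Mis-slope at Week 78: m = b78 − b_c.
- Residual Week 78 variance with the by-visit term: V = 48.485 − 6.7² × b78².
- Variance with the common slope: V + 6.7² × m².
- Variance inflation: 6.7² × m²/V.

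**Assumed inputs (not in the documents).** Slopes are linear in time between the Week 13 and Week 78 values shown. Total SDs are either flat at 6.963 or rising (4.0, 4.6, 5.9, 6.963). Correlation is compound symmetry 0.5 or 0.7, or autoregressive 0.6 or 0.8 per 26 weeks. Residual SDs are the total SDs less the part due to baseline. Power is for 3.0 points with 125 per arm.

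| Slope, Week 13 to Week 78 | Inflation, flat SDs | Inflation, rising SDs | Power with by-visit term | Power with common slope |
|---|---|---|---|---|
| 0 to 0 | 0% | 0% | 92.6% | 92.6% |
| −0.10 to +0.10 | 1% | 3-5% | 92.8% | 91.6-92.6% |
| −0.15 to +0.20 | 3-4% | 8-16% | 93.5% | 89.6-92.8% |
| −0.20 to +0.35 | 6-8% | 22-44% | 95.1% | 85.5-93.9% |
| −0.10 to +0.40 | 5-6% | 17-35% | 95.8% | 88.7-95.0% |

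**Most extreme cell in full** (−0.20 to +0.35, rising SDs, compound symmetry 0.7): b_c = −0.296, so m = 0.646. V = 48.485 − 44.89 × 0.1225 = 42.99. The added variance is 44.89 × 0.646² = 18.73, and 18.73/42.99 = 44%. The SE goes from sqrt(2 × 42.99/125) = 0.829 to sqrt(2 × 61.72/125) = 0.994, and power from 95.1% to 85.5%. If residual rather than total SDs are held at the stated values, the top of the flat range moves from 8% to about 10% and this cell becomes 43% (power 85.7%).

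**Which visits set the slope.** Using the SDs above directly in S, with flat SDs Weeks 13 and 26 together carry 0.46 to 0.50 of the weight and Week 78 carries 0.25 to 0.43. With rising SDs the two early visits carry about 0.8 to 1.3, and Week 78 −0.22 to +0.14.

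**Precision loss and imbalance shift are one quantity.** The SE of a chance baseline imbalance is 6.7 × sqrt(2/150) = 0.77 points with 150 per arm, or 6.7 × sqrt(2/125) = 0.85 with 125. Each point of imbalance moves the Week 78 estimate by m. For −0.20 to +0.35, rising SDs and autoregressive 0.8, m = 0.563. Then (0.563 × 0.85)² = 0.23, and the contrast variance is 2 × 42.99/125 = 0.69. The ratio, 0.33, is the variance inflation itself. Across unequal-slope scenarios a 1-SE imbalance shifts the estimate by about 0.1 to 0.5 points.

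**Check by simulation.** Full-likelihood fits: 300 randomized, 17% random dropout, rising SDs, autoregressive 0.8, 600 runs per scenario, stratification factors omitted. Empirical SE, common versus by-visit slope:
- zero slopes: 0.817 versus 0.819;
- −0.15 to +0.20: 0.875 versus 0.833;
- −0.20 to +0.35: 0.923 versus 0.805, with power 89.8% versus 96.3%.

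In the steepest scenario both models averaged 3.02 points for a true 3.0. Under no effect they rejected 5.5% and 5.7% of the time; the Monte Carlo SE is sqrt(0.055 × 0.945/600), about 0.9 points.

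**The case against.** The strongest reply is that the specified model is pre-specified, consistent across text, table and code, and valid, so this is only an efficiency refinement of unknown size. Most of that stands. Nothing in the documents fixes the slopes, the early SDs or the correlations. Randomization is stratified by MMSE group, which is related to baseline ADAS-Cog 13, so real imbalance should be smaller than the simple-randomization SE. The 325 subjects actually randomized also bring that SE down to 6.7 × sqrt(2/162.5) = 0.74. For A-IADL-W and CDR-SB no inputs exist, so no size can be given.

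A reader might infer that the early visits always dominate the pooled slope. That holds only if variance grows over visits, which is plausible but not stated.

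A reader might also count lost precision and uncorrected imbalance as two harms. The arithmetic above shows that they are the same one.

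Finally, the imputation regressions in 8.3.2 use BASE as a predictor at each visit, so they allow visit-specific slopes that the MMRM fitted afterwards does not. It is tempting to call this an error. An imputation model richer than the analysis model is not wrong in itself, and the code is an example for a sensitivity analysis.

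What the reply does not answer is that equality of slopes is assumed, never examined, and costs almost nothing to relax.

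**Conclusion.** The point holds as a precision improvement, conditional on unequal slopes. The variance inflation at Week 78 is 0% with equal slopes, about 1-8% with flat SDs and about 3-44% with rising SDs. The corresponding loss is roughly 0 to 9 power points for 3.0 points, and 9.6 (95.1% to 85.5%) in the single most extreme cell. All non-zero figures rest on assumed slopes and covariances.

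Three stronger readings are not supported. The primary test is not invalid: simulated type I error was near 5% under both models. The treatment estimate is not biased on average under randomization; imbalance moves it in a given trial, in either direction. And the stated power is not wrong: it is a two-sample calculation on the unadjusted change SD, it reproduces, and it does not depend on this model term. Some steep-slope scenarios would put the specified model below 90%, but those are assumptions and not a finding about this trial.

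**What to change.** Before unblinding, add the baseline ADAS-Cog 13-by-visit interaction (BASE*VISIT) to the model in SAP 8.3.1, to Table 16 and to the example MODEL statement in 8.3.2. In 8.3.3, add each endpoint's own baseline-by-visit term for A-IADL-W, CDR-SB and the other endpoints analysed by MMRM.

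The cost is 3 degrees of freedom for ADAS-Cog 13 (four visits) and 2 for each key secondary (Weeks 26, 52 and 78), plus one line in each program. No new data are needed. With equal slopes essentially nothing is lost (simulated SE 0.819 against 0.817). If the primary model is to stay as written, the minimum is to pre-specify the by-visit version as a sensitivity analysis.

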8.3.2 Supportive and Sensitivity Analyses of the Primary Efficacy Endpoint

Supportive Analyses

As supportive analysis, the primary endpoint will be analyzed using the MMRM model on the per-protocol population and on completers. Additional supportive analyses may include MMRM with Last Observation Carried Forward (LOCF).

Additional supportive analyses will include the repetition of the primary analysis using the 'while-on-treatment' strategy on the FAS population. This strategy estimates the treatment effect before the occurrence of intercurrent events. These events include treatment discontinuation and the use of symptomatic AD medications (AChE inhibitors or memantine). Any data collected after the occurrence of intercurrent events will be considered as missing.

Sensitiviy Analyses

Multiple Imputations (Missing at Random, MAR)

As a sensitivity analysis, a similar MMRM model as the one applied to the primary endpoint analysis will be repeated using multiple imputation methods under the assumption of MAR.

Before conducting the multiple imputation, the missing data pattern will be examined. A dataset is said to have monotone missing pattern if the missing values always occur at the end of the longitudinal data, e.g., missing data after withdrawal.

A dataset is said to have non-monotone missing pattern if some subjects have missing values for intermediate visits but have available data at subsequent visits. If the ADAS-Cog data are deemed having monotone missing pattern, the standard multiple imputation approach using SAS PROC MI with regression method will be applied. If ADAS-Cog data are determined to have non-monotone missing pattern, the Markov Chain Monte Carlo (MCMC) method will first be applied to impute the intermittent missing data, and then the regression method will follow to impute the monotone missing data. In the case that the regression method cannot fully impute the missing data, the MCMC method will be applied to impute both monotone and non-monotone missing patterns. The example SAS programming codes using regression method for monotone missing pattern are:

```
PROC MI DATA=DATAIN OUT=DATAOUT NIMPUTE=100 SEED=999[to be changed]; CLASS TREATMENT ACHEI AGEGRP GENDER DISSTAGE; VAR TREATMENT ACHEI AGEGRP GENDER DISSTAGE BASE ...; [insert scheduled visits for ADAS-Cog 13 up to Week 78, i.e, V5 V7 ...] MONOTONE REGRESSION; RUN;
```

The example SAS programming codes using MCMC method for non-monotone missing pattern, follow by regression method for monotone missing pattern are:

```
PROC MI DATA=DATAIN OUT=DATAOUT MONO NIMPUTE=100 SEED=999[to be
changed];
CLASS TREATMENT ACHEI AGEGRP GENDER DISSTAGE;
VAR TREATMENT ACHEI AGEGRP GENDER DISSTAGE BASE ... ; [insert
scheduled visits for ADAS-Cog 13 up to Week 78, i.e, V5 V7 ....
MCMC CHAIN=MULTIPLE IMPUTE=MONOTONE;
PROC SORT DATA=DATAOUT MONO;
BY IMPUTATION TREATMENT;
RUN;
PROC MI DATA-DATAOUT MONO OUT-DATAOUT REG SEED-999[to be changed]
NIMPUTE=1;
BY IMPUTATION;
CLASS TREATMENT ACHEI AGEGRP GENDER DISSTAGE;
VAR TREATMENT ACHEI AGEGRP GENDER DISSTAGE BASE ... ; [insert
scheduled visits for ADAS-Coq 13 up to Week 78, i.e, V5 V7 ...]
MONOTONE REGRESSION;
RUN;
```

The changes from baseline at all visits will be calculated from the imputed 100 sets of data. The MMRM model will be examined for each set of data. The results from the 100 sets of data will be combined via Rubin's rule to produce estimated LSMs and 95% CIs that incorporate the uncertainty from missing data. PROC MIANALYZE will be used. The example SAS programming codes are:

```
PROC SORT DATA=DATAOUT_REG;

BY _IMPUTATION_ TREATMENT;

RUN;

PROC MIXED DATA=DATAOUT_REG;

BY _IMPUTATION_;

CLASS TREATMENT(REF='PLACEBO') ACHEI AGEGRP GENDER DISSTAGE;
```

```
MODEL CHG =TREATMENT ACHEI AGEGRP GENDER DISSTAGE BASE VISIT TREATMENT*VISIT/SOLUTION;
REPEATED VISIT/SUBJECT=USUBJID TYPE=UN;
LSMEANS TREATMENT*VISIT /ALPHA=0.05 PDIFF CL;
ODS OUTPUT LSMEANS=LS DIFFS=LSDIFF;
RUN;
PROC SORT DATA=LSDIFF;
by _IMPUTATION_;
RUN;
PROC MIANALYZE PARMS(CLASSVAR=FULL) = LSDIFF;
CLASS TREATMENT;
MODELEFFECTS TREATMENT*VISIT;
ODS OUTPUT PARAMETERESTIMATES=DIFF_MI;
RUN;
```

Multipe Imputations (Missing Not at Random, MNAR)

Additional sensitivity analysis may be provided to evaluate the robustness of inferences on the same estimand, to assess deviations from the assumptions used in the statistical model, and to address limitations in the data. The possibility of "missing not at random" (MNAR) data will also be considered. After all active subjects complete the study and database is locked, the unblinded data will be examined and the missing data pattern evaluated. Based on the missing data mechanisms in the FAS, other multiple imputations methods will be explored to select the most appropriate methods. These methods may include the "Placebo-Based Pattern-Mixture model" or the "Tipping-Point Method". These sensitivity analyses will be described and documented in the final CSR.

Other Supportive or Sensitivity Analyses

Additional supportive or sensitivity analyses using observed data only (OC analysis), may be performed. For vMRI analyses, a model of slope analysis may also be conducted (Chen 2018; McDade 2022).

If any deaths occur, the worst-rank score method (Lachin 1999) will be employed as a supportive analysis. Any missing data due to deaths would be treated as the worst outcome in the primary analysis. This method makes no assumptions about the distribution. The observed changes from baseline at Week 78 in ADAS-Cog 13 scores from both the ALZ group and the placebo group will be combined and ranked from the lowest to the highest. Since a higher score in ADAS-Cog 13 indicates more severe impairment, the scores for all deaths will be assigned the highest rank. This analysis will be performed for the Week 78 observed cases data. The Wilcoxon Rank Sum Test and Hodges-Lehmann estimate will then be used to assess the treatment differences, and their 95% confidence intervals based on the Hodges-Lehmann estimates will also be provided.

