5.2.2 Additional Secondary Efficacy Endpoints

The additional secondary efficacy endpoints are:

- The CBL to Week 78 in ADAS-Cog 11
- The CBL to Week 78 in DAD
- The CBL to Week 78 in NPI
- The CBL to Week 78 in MMSE
- The CBL to Week 78 in QoL-AD
- The CBL to Week 78 in RUD Lite
- The CBL to Weeks 13, 26, and 52 in ADAS-Cog 13 and ADAS-Cog 11 scores
- The CBL to Weeks 26 and 52 in A-IADL-W, CDR-SB, DAD, and NPI scores
- The CBL to Weeks 13, 26, 39, 52, and 65 in MMSE scores

The CBL to Week 52 in QoL-AD (subject and informant) and RUD Lite scores

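### The missing-at-random imputation check of the primary endpoint uses only the primary MMRM's own variables and no post-baseline MMSE, so it largely repeats the MMRM

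*SAP*

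**What the plan says.** **The check.** SAP 8.3.2 states that "a similar MMRM model as the one applied to the primary endpoint analysis will be repeated using multiple imputation methods under the assumption of MAR". Both example PROC MI programs, for monotone and for non-monotone data, begin with "VAR TREATMENT ACHEI AGEGRP GENDER DISSTAGE BASE" and then take the ADAS-Cog 13 visits: "insert scheduled visits for ADAS-Cog 13 up to Week 78, i.e, V5 V7". No other post-baseline scale is listed, and the text names no auxiliary variable. The MMRM fitted after imputation has the same covariates and an unstructured covariance ("REPEATED VISIT/SUBJECT=USUBJID TYPE=UN").

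**The primary analysis.** SAP 8.3.1 fits an MMRM with treatment, AChEI use, age group, gender, baseline MMSE category (26 or below against above 26), baseline ADAS-Cog 13, visit and treatment by visit. It also assumes MAR. ADAS-Cog 13 is measured at baseline and Weeks 13, 26, 52 and 78.

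**MMSE.** SAP 5.2.2 lists Week 78 and "The CBL to Weeks 13, 26, 39, 52, and 65 in MMSE scores". MMSE is also collected at the early-termination visit (Protocol 7.2.14) and at retrieved-dropout visits, which take place only at Weeks 52 and 78 (Protocol 7.2.15).

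**Other missing-data analyses.** SAP 8.3.2 names placebo-based and tipping-point methods only as possibilities, to be chosen after lock on unblinded data. The imputation from retrieved dropouts in Protocol 10.7.2 does not reappear in SAP 8.3.2.

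**The concern.** A sensitivity analysis should be able to disagree with the primary one. With the same variables and the same MAR assumption, imputation followed by the MMRM tends to the MMRM's own answer as the number of imputations grows. Small differences remain, for example because the imputation regressions let stratum and baseline effects vary by visit.

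Imputation can add something by using post-baseline information that is outside the analysis model. Here that information exists. ADAS-Cog 13 has two 26-week gaps (Weeks 26 to 52 and 52 to 78), and MMSE is measured inside both. Protocol 5.5 lists loss of capacity to consent after cognitive decline, and a need for memantine, among the reasons for withdrawal. If dropout follows decline that MMSE has recorded and ADAS-Cog has not, MAR given both scales is more plausible than MAR given ADAS-Cog 13 and baseline data. The stake is how much reassurance the only fully specified imputation check can give.

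**Working it through.** **1. Calibration against the plan's own figure.** SAP 4.1 gives SDs of change of 5.6 (placebo) and 8.1 (active), with 125 completers per arm. Root-mean-square SD = √((8.1² + 5.6²)/2) = 6.963. SE = 6.963 × √(2/125) = 0.881. For 2.5 points, 2.5/0.881 = 2.84 and power is 81.0% (SAP: about 80%). For 3 points it is 92.6% (SAP: above 90%). The plan's figures reproduce, and 6.96 was used as the SD in step 3.

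**2. Variables side by side.**

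| | Primary MMRM | MAR imputation model |
|---|---|---|
| Treatment, AChEI, age group, gender | yes | yes |
| Baseline MMSE category | yes | yes (DISSTAGE is taken to be this stratum) |
| Baseline ADAS-Cog 13 | yes | yes |
| ADAS-Cog 13, Weeks 13, 26, 52, 78 | yes | yes |
| Post-baseline MMSE | no | no |
| Assumption | MAR | MAR |

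**3. Simulation.** 300 subjects, 1:1, true difference −2.5 (negative favours ALZ-801). Three analyses: the MMRM, imputation as planned, and imputation with MMSE at Weeks 13, 26, 39, 52, 65 and 78 added. Assumptions that are not in the documents: the size of the correlation r between ADAS-Cog and MMSE change (0.4 to 0.7), visit noise, the dropout mechanism, and no early-termination scores. Main runs (the first had 100 trials and 100 imputations, the others 150 trials and 30):

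| Assumed dropout | Rate | MMRM | As planned | With MMSE | Mean abs. gap to MMRM, as planned / with MMSE |
|---|---|---|---|---|---|
| Random, r = 0.55 | 17.0% | −2.678 | −2.673 | −2.677 | 0.041 / 0.071 |
| Follows ADAS-Cog, r = 0.55 | 15.9% | −2.445 | −2.441 | −2.457 | 0.048 / 0.068 |
| Follows last MMSE, active arm only, r = 0.55 | 17.3% | −2.794 | −2.791 | −2.522 | 0.053 / 0.273 |
| Same, r = 0.7 | 17.3% | −2.807 | −2.811 | −2.574 | 0.051 / 0.235 |

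Over all settings, the planned imputation and the MMRM correlated 0.993 to 0.998, with SEs within 3% (for example 0.852 against 0.846). Adding MMSE left the SE essentially unchanged.

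*Precision.* Each mean in row 3 has Monte Carlo SE of about 0.83/√150 = 0.07, so rows should be read across rather than against −2.5. The paired shift is much more precise. With SDs 0.826 and 0.831 and correlation 0.990, the SD of the difference is √(0.826² + 0.831² − 2 × 0.990 × 0.826 × 0.831) = 0.117, and 0.117/√150 = 0.01. The shift in row 3 is 2.794 − 2.522 = 0.27, about a third of one SE (0.27/0.84 = 0.32).

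*A less favourable run.* With r = 0.4, 28.6% dropout and 60 trials, adding MMSE moved the mean from −2.729 to −2.258, past the true value. Monte Carlo SE is 0.777/√60 = 0.10, so that run does not settle which estimate is closer.

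**4. Two further simulations with early-termination scores.**
- True benefit 3.0, correlation about −0.68, about 17% dropout, 60% of dropouts with an early-termination visit, decline-driven dropout on placebo only: bias −0.31 without MMSE and −0.24 with it. Without early-termination scores: −0.40 and −0.27. Same mechanism in both arms: −0.11 and −0.08.
- MMSE ceiling, 60% early-termination visits assigned by the SAP windows, 9% to 26% dropout: bias fell from about 0.33–0.45 to 0.00–0.12 point when dropout followed MMSE in one arm, and from 0.29–0.36 to about 0.24 when it followed latent decline in one arm. Otherwise nothing material changed.

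The direction depends on the arm: losing decliners from the active arm overstates benefit, and losing them from placebo understates it.

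**5. How many subjects this touches.** In the random run, 5.4% of subjects had a Week 39 or 65 MMSE later than their last ADAS-Cog 13. That is 0.054/0.170 = 32% of dropouts, or 0.054 × 300 = 16 subjects, before any early-termination scores are counted.

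**6. Missing-data pattern with MMSE added.** A subject who stops drug soon after Week 26 and attends both retrieved-dropout visits has ADAS-Cog 13 at all four visits but usually no MMSE at Weeks 39 and 65. Windows also differ. MMSE fits SAP Table 3 and ADAS-Cog fits Table 5, so an early-termination visit on day 300 is Week 39 for MMSE (days 229–319) and Week 52 for ADAS-Cog (days 275–456). The extended list is therefore often non-monotone.

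**The case against.** - **A MAR imputation that mirrors the MMRM is a legitimate computational check, and the code is labelled as an example.** This stands: no error or contradiction is shown, and auxiliaries are not forbidden. But none is pre-specified either.
- **Early-termination scores shrink the gap.** This stands. The early-termination visit includes ADAS-Cog, and from day 457 the score counts as Week 78, which leaves nothing to impute. The gain comes mainly from subjects with no such visit.
- **The gain is small and depends on the mechanism.** This stands. With random or ADAS-driven dropout, imputation with MMSE also tracks the MMRM (correlation 0.991 to 0.995). In the less favourable decline scenarios most of the bias remains (0.24 of 0.31).
- **Protocol 5.5 gives no rate for decline-related withdrawal.** This stands. It is one permitted reason among many.
- **Informative dropout is handled elsewhere.** This stands in part. Off-treatment data are included and Week 78 collection is given priority (SAP 8.3.1), but the MNAR methods are optional and chosen after unblinding.

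A reader might infer that the imputation rests on ADAS-Cog 13 alone, or that the plan ignores the MMSE. The documents do not support that: treatment and all four strata are in the model, and one stratum is the baseline MMSE category. A reader might also infer that MMSE can be added without disturbing the monotone pattern or at no cost. The retrieved-dropout schedule and the differing windows rule that out.

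**Conclusion.** The point holds in a limited form. As written, the MAR imputation uses the MMRM's own variables and assumption, so its agreement with the primary result says little about robustness. Post-baseline MMSE is already collected and goes unused.

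Under assumed decline-related dropout, adding it reduced bias by about 0.03 to 0.4 point. The low end applies when both arms follow the same mechanism, and the high end when dropout follows MMSE in one arm only. If dropout is random or explained by ADAS-Cog 13, the gain is about nil. These sizes rest on an assumed correlation, assumed dropout mechanisms and assumed early-termination attendance, none of which the documents give.

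This does not show that the primary MMRM is biased, and the fix does not replace a pre-specified MNAR analysis. It is a cheap improvement.

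**What to change.** In SAP 8.3.2, pre-specify MMSE scores at Weeks 13, 26, 39, 52, 65 and 78 as auxiliary variables in the imputation model, interleaved with the ADAS-Cog 13 visits in time order. State that they enter the imputation only and that the MMRM fitted afterwards is unchanged.

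Two details need to go with it:
- Expect a non-monotone pattern. Apply the plan's existing step for non-monotone data first, then the regression step.
- Order the two scales by actual assessment date, or put them on common windows for the imputation, so that one early-termination visit is not treated as two different times.

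The cost is a longer variable list in code that is already planned, a larger imputation model, more reliance on the non-monotone step, and a test run on dummy data before lock. No new data are needed.
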